2 STUDY OBJECTIVES

The objectives of the study and corresponding study endpoints are detailed in [Table 1](#).

Table 1: Objectives and Related Endpoints

Objective	Endpoint	Analysis
Primary		
• To determine the safety and tolerability profile of CD388 Injection when dosed either by intramuscular (IM) or subcutaneous (SQ) administration as a single dose to healthy adult subjects.	Incidence and severity of treatment-emergent adverse events (TEAEs), including but not limited to adverse events (AEs) and serious adverse events (SAEs) (including systemic reactogenicity/ injection site reactions and hypersensitivity reactions), AEs leading to study drug discontinuation and/or study withdrawal, vital signs, 12-lead electrocardiograms (ECGs), and clinical laboratory tests (including hematology, coagulation, serum chemistry, and urinalysis), after a single dose of CD388.	Refer to Section 8
Secondary		
• To determine the plasma pharmacokinetic (PK) profile of CD388 Injection when dosed either by IM or SQ administration following a single dose and a repeated single dose to healthy adult subjects.	• Pharmacokinetic parameters following CD388 Injection administration: maximum plasma concentration (C_{max}), time to maximum plasma concentration (T_{max}), terminal elimination half-life ($t_{1/2}$), apparent clearance (CL/F), apparent volume of distribution (V_z/F), area under the plasma concentration-time curve from time 0 to time of last quantifiable sample (AUC_{0-t}), area under the plasma concentration-time curve from time 0 extrapolated to infinity ($AUC_{0-\infty}$).	Refer to Section 7

Objective	Endpoint	Analysis

 To determine the safety and tolerability profile of CD388 Injection when dosed either by IM or SQ administration as a repeated single dose (after washout of 3 months or 5 effective half-lives from the first dose; whichever is longer) to healthy adult subjects. 	
 Incidence and severity of TEAEs, including but not limited to AEs and SAEs (including systemic reactogenicity/injection site reactions and hypersensitivity reactions), AEs leading to study drug discontinuation and/or study withdrawal, vital signs, ECGs, and clinical laboratory tests (including hematology, coagulation, serum chemistry, and urinalysis), after a repeated single dose of CD388. 	Refer to Section 8
Exploratory		

 To determine the PK profile of CD388 Injection in upper respiratory tract after IM or SQ administration as a single dose to healthy adult subjects. 	
 Pharmacokinetic parameters following CD388 Injection administration: maximum nasopharyngeal (NP) concentration (C_{max}), time to maximum NP concentration (T_{max}), area under the NP concentration-time curve from time 0 to time of last quantifiable sample (AUC_{0-t}). 	Refer to Section 7

 To identify CD388 metabolites in plasma, CD388 and its metabolites in urine, and CD388 drug-antibody ratio (DAR) distribution in plasma, and CD388 glycoforms in serum after IM or SQ administration to healthy adult subjects. 	
 CD388 metabolites (e.g., free zanamivir, zanamivir dimers) in plasma and urine, CD388 in urine and nasal wash, CD388 DAR distribution in plasma, and CD388 glycoforms in serum, to be reported separately. 	Refer to Section 7

 To evaluate biomarkers that may be associated with AEs after CD388 Injection. 	
 Results of the analyses of exploratory biomarkers (including but not limited to cytokines, chemokines, acute phase reactants, etc.). 	Refer to Section 9

 To evaluate CD388 immunogenicity. 	
 Anti-drug antibody titers in blood (plasma or serum). 	Refer to Section 9

 To explore pharmacogenomics related to CD388. 	
 Results of the analyses of pharmacogenomic samples, to be reported separately. 	Refer to Section 9

Objective	Endpoint	Analysis

 • To explore the effects on cardiac safety in subjects administered CD388 Injection. 	
 • 12-lead ECG and Holter monitoring parameters. 	Refer to Section 8

 • To explore the effect of CD388 injection on the occurrence of influenza-like illness (during flu season). 	
 • Influenza-like illness reporting during the outpatient follow-up period. 	Refer to Section 8

3 STUDY DESIGN

3.1 General Description

This is a first-in-human (FIH), Phase 1, single-center, prospective, randomized, double-blind study of ascending single doses of CD388 Injection administered IM or SQ to healthy adult subjects followed by another single dose of CD388 Injection administered by the same route 3 months or 5 effective half-lives, whichever is longer, after the first dose in the middle and high dose groups (dosing may be adjusted for tolerability). The goals are to assess safety, tolerability, immunogenicity (anti-drug antibodies [ADA]), and PK of CD388.

Dose levels of CD388 to be assessed will follow an ascending single dose design with the starting dose based on findings from 3-month rat and monkey toxicology studies. Within each route (IM and SQ dose, route assignment is unblinded), subjects will be randomized to receive a single dose of CD388 Injection or saline placebo (treatment assignment is blinded) according to the design. It should be noted that each cohort will be divided into 2 groups identified as “sentinel” groups (randomized 1:1) and “main” groups (randomized 7:2):

- Low dose level: Cohort 1A (IM) and Cohort 1B (SQ) – each route n = 2 sentinel and n = 9 main
- Mid dose level: Cohort 2A (IM) and Cohort 2B (SQ) – each route n = 2 sentinel and n = 9 main
- High dose level: Cohort 3A (IM) and Cohort 3B (SQ) – each route n = 2 sentinel and n = 9 main
- Highest dose level: Cohort 4B (SQ) – n = 2 sentinel and n = 9 main

For each route, the sentinel or first group of 2 subjects (1 CD388: 1 placebo) at a dose level will be administered blinded study drug and closely monitored for safety for at least 1 week. If no drug-related SAEs or drug-related Grade ≥ 3 AEs have occurred, the subjects in the corresponding main group may be dosed within 24 hours. The observation duration may be adjusted for the sentinel groups in Cohorts 2A, 2B, 3A, 3B, and 4B based on data from previous cohorts.

Subjects in Cohort 4B will receive a single dose of CD388 or placebo. Subjects in Cohorts 2A and 2B and Cohorts 3A and 3B will receive a second single dose of CD388 Injection or placebo after washout of 3 months or 5 effective half-lives, whichever is longer, after the first dose if it is determined that the safety and tolerability of the first dose is acceptable upon review of the cumulative safety data.

Immediately prior to the second single dose, within each dose and route, any dropouts in the sentinel groups will be randomly replaced with subjects from the main groups, retaining their original treatment assignment (i.e., subjects assigned to placebo will remain placebo, and subjects assigned to CD388 will remain CD388; this may require unblinded personnel to oversee).

All subjects will be admitted to the clinical research unit (CRU) for observation and safety assessments from Day -1 (check-in) to Day 30.

Table 2: Study Cohorts

Dose (mg)	Number of Subjects (N = 77)					
	Intramuscular (IM)			Subcutaneous (SQ)		
	Cohort	CD388 (n = 24)	Placebo (n = 9)	Cohort	CD388 (n = 32)	Placebo (n = 12)
50	Cohort 1A (sentinel)	1	1	Cohort 1B (sentinel)	1	1
50	Cohort 1A (main)	7	2	Cohort 1B (main)	7	2
150	Cohort 2A (sentinel)	1	1	Cohort 2B (sentinel)	1	1

150	Cohort 2A (main)	7	2	Cohort 2B (main)	7	2
450	Cohort 3A (sentinel)	1	1	Cohort 3B (sentinel)	1	1
450	Cohort 3A (main)	7	2	Cohort 3B (main)	7	2
900	NA	NA	NA	Cohort 4B (sentinel)	1	1
900	NA	NA	NA	Cohort 4B (main)	7	2

NA= Not Applicable

Note: Immediately prior to the second single dose, within each dose and route, any dropouts in the sentinel groups will be randomly replaced with subjects from the main groups, retaining their original treatment assignment (i.e., subjects assigned to placebo will remain placebo, and subjects assigned to CD388 will remain CD388).

3.2 Investigational Product

The investigational product (IP) CD388 will be provided by the Sponsor. The placebo, normal saline, will be sourced by the site.

3.3 Study Procedures

For complete details on the study assessments to be performed for each study period, refer to [APPENDIX A](#) for Cohort 1A to 3B and [APPENDIX B](#) for Cohort 2A to 3B.

3.4 Randomization and Unblinding Procedures

After informed consent has been obtained, subjects will be screened for study eligibility before randomization.

Within each route (IM and SQ dose, route assignment is unblinded), subjects will be randomized to receive a single dose of CD388 Injection or saline placebo (study drug assignment is blinded). The study site's pharmacist (or pharmacist designee) will obtain the study drug assignment by a manual paper transaction. A subject is considered randomized when the randomization transaction is recorded in the subject's source documents.

All study personnel (including the Sponsor, Investigator, and site personnel directly involved in study conduct) and subjects will remain blinded to study drug assignment until the study is completed and the final database is locked with the exception of the pharmacy personnel, pharmacy monitor, and unblinded Sponsor personnel (such as Data Review Committee, clinical supply manager, bioanalytical, PK lead, and quality manager) who may be unblinded to study medication at any time during study conduct. The pharmacy monitor will monitor study drug preparation and accountability during the study and cases in which unblinding is required due to a safety or tolerability issue. To maintain study blinding, study drug preparation will be performed by an unblinded site pharmacist (or qualified unblinded personnel at the study site not involved with study procedures or evaluations).

4 ANALYSIS POPULATIONS

The following populations will be defined:

- **Enrolled Population:** All subjects who provide informed consent and are randomized.
- **Safety Population:** The safety population will include all randomized subjects who receive any amount of study drug.
- **Pharmacokinetic Population:** The PK population will include all randomized subjects who have received at least a portion of 1 dose of CD388 and have at least 1 evaluable postdose concentration value. Subjects administered matching placebo will not be included in the PK population.

Pharmacokinetic Completer Population: [Dose Groups 2A, 2B, 3A, and 3B only] The PK population will include all randomized subjects who have received 2 single doses of CD388 and obtained PK samples at all visits.

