Abbreviations: AEs = adverse events; BMI = body mass index; BP = blood pressure, CBC = complete blood count; COVID-19 = coronavirus disease 2019; CRU = clinical research unit; DAR = drug-antibody ratio; ECG = electrocardiogram; FSH = follicle-stimulating hormone; HBV = hepatitis B virus; HCV = hepatitis C virus; HIV = human immunodeficiency virus; HR = heart rate; hr = hour; ICF = informed consent form; OV = outpatient visit; PK = pharmacokinetic; RR = respiration rate; SARS-CoV-2 = severe acute respiratory syndrome coronavirus 2.

Schedule of Events: First Single Dose, Cohorts 1A, 1B, 2A, 2B, 3A, and 3B

- For subjects in Cohorts 1A and 1B: outpatient visits will occur at Day 45 (OV1), Day 60 (OV2), Day 90 (OV3), and Day 120 (OV4). For subjects in Cohorts 2A, 2B, 3A, and 3B, timing of outpatient visits will occur at Day 45 (OV1), $\sim 2 \times t_{1/2}$ (OV2), $\sim 3 \times t_{1/2}$ (OV3), and $\sim 4 \times t_{1/2}$ (OV4), pending PK data from Cohorts 1A and 1B. If 2 half-lives have passed by OV2, the visit may be omitted.
- For subjects who discontinue study early, the OV4 procedures should be performed.
- For subjects in Cohorts 2A, 2B, 3A, and 3B, reconfirmation of inclusion and exclusion criteria (retesting of FSH not required) is to be completed at second single dose period's CRU check-in and prior to the second single dose of CD388 Injection or placebo.
- On Day 1, the targeted physical examination should be performed predose. Vital signs collection will occur predose, 6 hours postdose, and as clinically indicated.
- 12-lead ECG is to be performed at screening, at CRU check-in on Day -1, predose (immediately prior to study drug administration) and 6 hours postdose (± 10 minutes) on Day 1, and as indicated in the Schedule. Subjects are to be resting and semi-recumbent when ECG is being conducted.

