1.1.2. Second Single Dose, Cohorts 2A, 2B, 3A, and 3B

Table 2: Schedule of Events: Second Single Dose, Cohorts 2A, 2B, 3A, and 3B

Day (Window)	Clinical Research Unit (CRU) Inpatient Stay										Outpatient CRU Visits ^a			
	-1 (±10)	1	2	3-6	7	9	11	14	21	30	OV1 (±3)	OV2 (±5)	OV3 (±7)	OV4 ^b (±14)
Inclusion/Exclusion criteria ^c	X	X												
Complete physical with vital signs (BP, RR, HR, oral temperature, height, weight, BMI)	X													
Targeted physical with vital signs (BP, RR, HR, oral temperature)		X ^d	X	X	X			X	X	X	X	X	X	X
Safety ECG ^e	X	X			X					X				X
Laboratory evaluations (CBC with/platelets, serum chemistry, urinalysis)	X		X	X ^f	X			X	X	X	X	X	X	X
Virology screening (HBV, HCV, HIV)	X													
Virology screening (SARS-CoV-2)	X													
Urine Pregnancy ^g	X													
Drug/alcohol screen ^h	X													
Dosing of Study Drug (Cohorts 2 and 3 only)		X												
Reactogenicity/injection site inspection ⁱ		X	X	X										
PK sample collection ^j		X	X	X	X	X	X	X	X	X	X	X	X	X
Samples for metabolite identification ^k		X	X					X		X				X
Exploratory biomarker samples		predose		X ^f										
Anti-drug antibodies		predose						X		X	X	X	X	X
Nasopharyngeal swab/nasal wash collection ^l		predose	X	X	X	X	X	X	X	X				
Assess and record AEs ^m	X	X	X	X	X	X	X	X	X	X	X	X	X	X
Concomitant medications/procedures review ⁿ	X	X	X	X	X	X	X	X	X	X	X	X	X	X

Abbreviations: AEs = adverse events; BMI = body mass index; BP = blood pressure, CBC = complete blood count; COVID-19 = coronavirus disease 2019; CRU = clinical research unit; ECG = electrocardiogram; HBV = hepatitis B virus; HCV = hepatitis C virus; HIV = human immunodeficiency virus; HR = heart rate; hr = hour; ICF = informed consent form; PK = pharmacokinetic; RR = respiration rate; SARS-CoV-2 = severe acute respiratory syndrome coronavirus 2.

Schedule of Events: Second Single Dose, Cohorts 2A, 2B, 3A, and 3B

- a. For subjects in Cohorts 2A, 2B, 3A, and 3B: outpatient visits will occur at Day 45 (OV1), Day 84 (OV2), Day 126 (OV3), and Day 168 (OV4).
- b. For subjects who discontinue study early, the Day 168 procedures should be performed.
- c. Reconfirmation of inclusion and exclusion criteria (retesting of FSH not required) is to be completed at CRU check-in on Day -1 and prior to the second single dose of CD388 Injection or placebo on Day 1.

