- d. On Day 1, the targeted physical examination should be performed predose. Vital signs collection will occur predose, 6 hours postdose, and as clinically indicated.
- e. 12-lead ECG is to be performed at CRU check-in on Day -1, predose (immediately prior to study drug administration on Day 1) and 6 hours postdose (± 10 minutes), and as indicated in the Schedule. Subjects are to be resting and semi-recumbent when ECG is being conducted.
- f. Laboratory evaluations need to be performed once during the Day 3–6 interval.
- g. Urine pregnancy test is required for females of childbearing potential at CRU check-in on Day -1.
- h. Drug and alcohol screen is to be performed during the outpatient visits if vital signs are abnormal (see [Appendix 2](#)).
- i. At indicated visits, inspection of administration site and surrounding area will be performed twice daily (once between approximately 2–4 hours postdose, and once approximately 8–12 hours postdose), with any abnormal findings reported as AEs. Reactions will be rated according to the scale provided in [Table 7](#).
- j. Blood samples for PK analysis will be collected predose (-24 hour window); post-dose at 24 hours (± 30 minute window); 48 hours (± 1 hour window); 72, 96, 120, 144, 168 hours (each ± 2 hour window); and Days 9, 10, 11, 12, 14, 21, 30 (each ± 2 hour window). Postdose samples collected at outpatient CRU visits on Days 45, 60, 90, and 120 have the same windows (i.e., in \pm days) as the visits.
- k. Blood samples for metabolite identification (e.g., free zanamivir, zanamivir dimers) will be collected on Day 1 at 2 hours postdose, on Day 2 at 24 hours postdose, on Day 30, and on Day 90. Urine samples for metabolite identification will be collected on Day 1 from 0–48 hours, from 48–96 hours, and from 96–144 hours postdose, on Day 14 over a 24-hour period, and over a 24-hour period that starts on Day 29 and ends prior to CRU check-out on Day 30.
- l. Nasopharyngeal swab samples will be collected predose on Day 1, and on Days 2, 5, 7, 9, 11, 14, 21, and 30. Nasal wash collection will occur at the time of C_{max} as determined from the first single dose (approximately 144 hours after dosing).
- m. Adverse events (including influenza-like illness which will be tested for both COVID-19 and flu) will be collected for all subjects as indicated below:

Cohort	AE/SAE monitoring period from signing of Informed Consent Form:
1A, 1B	Through 4 months after the dose of study drug

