After all subjects at a dose level (for the IM cohorts and SQ cohorts separately) have completed study drug administration and have undergone protocol-specified procedures and assessments for ≥ 14 days, the PI and Sponsor will review blinded safety data, including AEs (including reactogenicity/injection site reactions and hypersensitivity reactions), vital signs, 12-lead ECGs, and clinical laboratory results (including hematology, coagulation, serum chemistry, and urinalysis) to determine the safety and tolerability of the study drug. The incidence and severity of AEs, and adverse changes in vital signs, clinical laboratory findings, and ECGs will be taken into consideration when determining safety and tolerability of study drug. Escalation between dose levels will be based on review of at least 14-day post-dose safety data. If the dose/route of administration is determined to be safe and well tolerated ≥ 14 days after dosing, the next cohort of subjects will be enrolled and randomized to receive the next higher dose level of CD388 Injection or placebo. The data cut-off time point for data review and dose escalation decision has been adjusted for Cohorts 2A, 2B, 3A, and 3B based on data from Cohorts 1A and 1B.

Table 5: Study Design

Dose (mg) ^a	Number of Subjects (N = 77)					
	Intramuscular (IM)			Subcutaneous (SQ)		
	Cohort	CD388 (n = 24)	Placebo (n = 9)	Cohort	CD388 (n = 32)	Placebo (n = 12)
50	Cohort 1A (sentinel)	1	1	Cohort 1B (sentinel)	1	1
50	Cohort 1A (main)	7	2	Cohort 1B (main)	7	2
150	Cohort 2A (sentinel)	1	1	Cohort 2B (sentinel)	1	1
150	Cohort 2A (main)	7	2	Cohort 2B (main)	7	2
450	Cohort 3A (sentinel)	1	1	Cohort 3B (sentinel)	1	1
450	Cohort 3A (main)	7	2	Cohort 3B (main)	7	2
900	NA	NA	NA	Cohort 4B (sentinel)	1	1
900	NA	NA	NA	Cohort 4B (main)	7	2

Abbreviation: NA = not applicable.

Note: Immediately prior to the second single dose, within each dose and route, any dropouts in the sentinel groups will be randomly replaced with subjects from the main groups, retaining their original treatment assignment (i.e., subjects assigned to placebo will remain placebo, and subjects assigned to CD388 will remain CD388).

Subjects in Cohort 4B will receive a single dose of CD388 Injection or placebo (SQ).

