7.1 Missing Values

Except for predose samples (prior to the first administration), the lack of concentration values due to failure to collect the sample, a lost or compromised sample, or due to the subject's early termination from the study will be considered missing in the dataset, and no imputation will be done. Predose samples, prior to the first administration, will be imputed with zero.

If the actual collection time of a postdose PK sample is unknown, but a valid concentration value has been measured, the sample will be set to missing in the PK analysis and will be excluded from descriptive statistics but will be presented in listings.

Subjects who do not complete the sampling schedule may be included in the PK analysis for only the PK parameters that are judged not to be affected by the missing sample(s).

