	CD388 50 mg (N = XX)	CD388 150 mg (N = XX)	CD388 450 mg (N = XX)	Pooled Placebo (N = XX)	CD388 50 mg (N = XX)	CD388 150 mg (N = XX)	CD388 450 mg (N = XX)	CD388 900 mg (N = XX)			
	Major xx (xx.x)	xx (xx.x)	xx (xx.x)	xx (xx.x)	xx (xx.x)	xx (xx.x)	xx (xx.x)	xx (xx.x)	xx (xx.x)		
...											
Date: VERSION - YYYY-MM-DD			Data Source: XXXX					Program Source: XXXXX.sas			

IM = Intramuscular; SQ = Subcutaneous

Note: Percentages are based on the number of subjects in the safety population as the denominator.

Table 14.2.6 Template T2.1: Pharmacokinetic Data of CD388– Plasma (Pharmacokinetic Population),

Table 14.2.1.1.1.x

Descriptive Statistics of Plasma CD388 Concentration Data Following a Single <ADMIN> of <DOSE> CD388 to Healthy Subjects (<COHORT>) (PK Population)

			Time (h)										
			0	2	4	12	24	48	72	696		
Cohort	Route of Administration	CD388 Dose (mg)	Concentration (Units)										
			N	Mean	SD	Min	Median	Max	CV%				
Lower Limit of Quantitation is xx.x (Units)													
NC: Not Calculated, NS: No Sample													

x = 1 through 8 for Cohorts 1A, 1B, 2A, 2B, 3A, 3B, and 4B and PK Completer Population (Cohorts 2A, 2B, 3A and 3B only)

<DOSE> = 50 mg, 150 mg, 450 mg, and 900 mg for Cohorts 1A/1B, 2A/2B, 3A/3B, and 4B, respectively.

<ADMIN> = Intramuscular Injection for Cohorts 1A, 2A, and 3A or Subcutaneous Injection for Cohorts 1B, 2B, 3B, and 4B.

<COHORT> = Cohorts 1A, 1B, 2A, 2B, 3A, 3B, and 4B.

Programming Note:

Table 14.2.1.1.2.x: "Descriptive Statistics of Plasma CD388 Concentration Data Following a Repeated Single <ADMIN> of <DOSE> CD388 to Healthy Subjects (<COHORT>)" will follow the same layout.

Table 14.2.2.1.1.x: "Descriptive Statistics of Nasopharyngeal CD388 Concentration Data Following a Single <ADMIN> of <DOSE> CD388 to Healthy Subjects (<COHORT>)" will follow the same layout.

Table 14.2.2.1.2.x: "Descriptive Statistics of Nasopharyngeal CD388 Concentration Data Following a Repeated Single <ADMIN> of <DOSE> CD388 to Healthy Subjects (<COHORT>)" will follow the same layout.

Table 14.2.7 Template T2.2: Pharmacokinetic Parameters Summaries of CD388– Plasma (Pharmacokinetic Population)

Table 14.2.1.2.1.x
 Descriptive Statistics of Plasma CD388 Pharmacokinetic Parameter Estimates Following a Single <ADMIN> of <DOSE> CD388 to Healthy Subjects (<COHORT>)
 (PK Population)

Cohort	Route of Administration	CD388 Dose (mg)		C _{max} (Unit)	T _{max} (Unit)	AUC _{0-t} (Unit)	...	Vz/F (Unit)

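### Read literally, the PK Completer definition excludes subjects who followed the protocol, and it cannot be applied cleanly in the second dosing period

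*SAP*

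**What the plan says.** SAP section 4 defines four populations. The PK Population needs any part of one CD388 dose and one evaluable postdose concentration. The PK Completer Population, for Cohorts 2A, 2B, 3A and 3B only, needs subjects to "have received 2 single doses of CD388 and obtained PK samples at all visits". The SAP gives no tolerance for a missed visit, no minimum sample set and no rule for permitted omissions.

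The schedules bear on this in two places.

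- **First dose** (protocol Table 1 footnote a, repeated in SAP Appendix A). For these cohorts OV2, OV3 and OV4 are placed at about 2, 3 and 4 half-lives, and then: "If 2 half-lives have passed by OV2, the visit may be omitted".
- **Second dose** (protocol Table 2, repeated in SAP Appendix B). Footnote a says "outpatient visits will occur at Day 45 (OV1), Day 84 (OV2), Day 126 (OV3), and Day 168 (OV4". Footnote j says "Postdose samples collected at outpatient CRU visits on Days 45, 60, 90, and 120 have the same windows".

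SAP 7.1 is more lenient about incomplete sampling in general: "Subjects who do not complete the sampling schedule may be included in the PK analysis", limited to parameters judged not to be affected.

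The table shells T2.1 and T2.2 number their tables 1 to 8. Seven are the cohorts and the eighth is "PK Completer Population (Cohorts 2A, 2B, 3A and 3B only".

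**The concern.** A completer set is meant to hold subjects whose data support a result in both periods. This one selects on attendance at every visit. Whether a subject belongs can turn on an optional visit that has little bearing on whether Cmax or AUC can be estimated. In the second period it can also turn on which of two lists of days is taken as the schedule.

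At stake is the content of the Completer tables. They could lose evaluable subjects from groups of 8, and membership might be settled by an interpretation made once the data are known. The loss would also be hard to see. SAP Table 3 promises counts for each analysis population, but the disposition shell (T1.1) and the population listing (L4.2) show only the Enrolled, Safety and PK populations.

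**Working it through.** **Size of the set.** Protocol Table 5 gives 1 sentinel and 7 main CD388 subjects per cohort. Seven cohorts give 7 × 8 = 56 on CD388 and 7 × 3 = 21 on placebo, total 77, which reproduces the plan's figures. The four repeat-dose cohorts give a Completer ceiling of 4 × 8 = 32.

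**Does an omitted OV2 spoil the profile?** Table 2 footnote l puts the first-dose Cmax at about 144 hours, inside the inpatient stay, so OV2 has no bearing on it. AUC is still bracketed by OV1 and the later OV3 and OV4 samples. A subject without OV2 can therefore have both parameters and still fail the definition. Because OV2 is itself placed at about 2 half-lives, the omission condition, as worded, is met almost by construction.

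**Second-dose days, paired in order:**

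| Visit | Visit day (window) | PK sample day | Gap |
|---|---|---|---|
| OV1 | 45 (±3) | 45 | 0 |
| OV2 | 84 (±5) | 60 | 24 |
| OV3 | 126 (±7) | 90 | 36 |
| OV4 | 168 (±14) | 120 | 48 |

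For OV2 to OV4 the gaps exceed the windows, so the windows do not reconcile the two lists.

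**Share qualifying when OV2 is held.** The documents give no missed-visit rate, so 2% and 5% are assumptions, with misses taken as independent. Each period has one inpatient stay and four outpatient visits, so k = 2 + 8 = 10. Share = (1 − q)^k:

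- q = 2%: 0.98^10 = 0.817, or 6.5 of 8
- q = 5%: 0.95^10 = 0.599, or 4.8 of 8

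These are shares of twice-dosed subjects; dropout before the second dose comes on top.

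**If the rule means every scheduled sample.** Each period has 19 samples, so k = 38:

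- q = 2%: 0.98^38 = 0.464, or 3.7 of 8
- q = 5%: 0.95^38 = 0.142, or 1.1 of 8

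The text says visits, so this is the less natural reading.

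**If OV2 is omitted for a share f of subjects and counts as a miss**, with no other loss, completers = 32 × (1 − f): 32, 24, 16, 8 and 0 at f = 0, 25, 50, 75 and 100%.

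**The case against.** The strongest reply is that little depends on this set. A reader might infer that the repeat-dose PK tables rest on it. They do not. SAP 7.5.1 and 10.2 place PK summaries on the PK Population, shells T2.1 and T2.2 carry that title, and the repeated-dose tables follow their layout. The Completer set is one added table in each series. The route, dose-proportionality and relative-bioavailability shells also use the PK Population. This stands.

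A reader might also infer that the secondary objective needs this set to pair first-dose and second-dose results. SAP 7.5.2 specifies no such paired comparison, and the PK Population already contains every twice-dosed subject with data. This also stands.

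Nor does SAP 7.1 strictly contradict section 4. It governs PK analysis generally, and a stricter subset can coexist with it. It does show that a parameter-level rule is already available.

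It is tempting to count all 26 schedule columns with PK sampling as separate chances to miss a visit. That is not justified: nine of the 13 per period fall within a single inpatient stay.

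Finally, omission is optional and exists only in the first-dose schedule, and the rule could be read as covering only visits actually held. If the omission clause was meant to refer to OV1 at Day 45, it would rarely apply. The second-dose days imply a half-life of 84/2 = 126/3 = 168/4 = 42 days (inferred, not stated), and 45/42 is only 1.07 half-lives. These readings are possible, but the SAP does not choose among them, and none removes the second-dose mismatch.

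**Conclusion.** The point holds as a minor one. Taken literally, the rule can exclude subjects who complied with the protocol and have evaluable Cmax and AUC, and it has no unambiguous application in the second period. The effect is confined to the Completer tables: the eighth in T2.1 and T2.2 and in the shells that follow them.

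Under the visit-level reading with OV2 held, the loss is moderate: about 18% of twice-dosed subjects at an assumed 2% missed per visit and about 40% at 5%. A reader might go further and conclude that the set will be empty or nearly so. The documents do not support that. Certain emptiness requires OV2 to be omitted for every subject and the permitted omission to be counted as a miss, and nothing says that any OV2 was omitted. Near-emptiness otherwise needs very widespread omission, or the sample-level reading with about 5% or more missing.

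The analysis concerned is supplementary, descriptive and secondary.

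**What to change.** - In SAP section 4, define the set as subjects who received both CD388 doses and have the evaluable parameter (Cmax or AUC) in both periods, judged parameter by parameter under SAP 7.1.
- State that a visit omitted as the protocol allows does not count as missed.
- Reconcile the second-dose visit days with the second-dose PK sample days in protocol Table 2 and SAP Appendix B.
- Add the set to the disposition table (T1.1) and the population listing (L4.2), so that its size is reported.

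The cost is a rewritten definition with one clarifying statement, a footnote correction and two shell edits. No new data are needed. The downside is that a few profiles with missing samples are retained.
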